First we screen potential participants to ensure they meet criteria for study enrollment. All participants will be drawn from completers of the study "Peripheral induction of inhibitory brain circuits to treat Tourette's: pilot," and we will draw much of the demographic and clinical information from the RCT. Participants will attend one session (whenever possible, in person at the same visit as the final study visit for the RCT), in which they will learn how to use the device and have it set to appropriate settings. They will then take the device home to use for four weeks, during which time they will fill out brief surveys whenever they turn the device on and off, as well as at two other points throughout the day. These surveys record tic intensity and frequency, as well as discomfort due to the device. Participants will also complete a more extensive survey at the conclusion of the study.

Recruitment

Participants will be recruited from completers of the study "Peripheral induction of inhibitory brain circuits to treat Tourette's: pilot."

First visit

1. We present an informed consent document to participants (to parents of potential child participants) explaining the study, risks and benefits of participation and that participation is voluntary. The ICD will be provided online prior to the initial visit. Potential subjects will review the informed consent document with the investigator or designee and will have opportunity to resolve questions or concerns. Adult participants will provide their own informed consent. For child participants, consent from one parent or guardian is sufficient, as the study is minimal risk. Children must assent to participate.
2. All data from the "Peripheral induction of inhibitory brain circuits to treat Tourette's: pilot" study will be imported for comparison with information collected during this study.
3. If more than 2 weeks have elapsed since the most recent administration of the Adult Tic Questionnaire (ATQ) [8,9], participants will be asked to repeat it.
4. Explain use of the TENS unit, including which settings may be changed by the participant and which settings should remain on the settings established by the investigator.

5. Attach electrodes.
6. Determine stimulation threshold (12 Hz, pulse width 200μs), starting at 0 and increasing slowly until a twitch of the thumb is seen.
7. Verify that the participant is able to set up and turn on the device on their own.

Online during study period

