1. Participants will complete online measures at the following times:
 - a. Turning on the stimulator
 - i. Tic intensity
 - ii. Tic frequency
 - b. Turning off the stimulator
 - i. Tic intensity
 - ii. Tic frequency
 - iii. Discomfort from stimulation
 - iv. Overall symptom improvement

Texts will be sent twice daily at predetermined times, and the participant will respond with times “c.” or “d.” below depending on stimulator use when the text is received:

- c. Answering a text, stimulator currently on
 - i. Tic intensity
 - ii. Tic frequency
 - iii. Discomfort from stimulation
 - iv. Overall symptom improvement
 - d. Answering a text, stimulator currently off
 - i. Tic intensity
 - ii. Tic frequency
2. Participants may be contacted throughout the study for reminders regarding compliance or assistance in troubleshooting issues with the device or surveys.

Online at conclusion of study

1. The study concludes 4 weeks (± 5 days) after the initial visit (or earlier, if the participant decides to stop treatment before 4 weeks).
2. We review the online questionnaires and collect the following additional measures:
 - a. Current symptom status
 - i. Adult Tic Questionnaire (ATQ) tic rating
 - ii. Premonitory Urge for Tics Scale (PUTS) [10]
 - b. Treatment efficacy and side effects
 - i. [Modified Clinical Global Impression – Efficacy Index](#)
 - ii. Patient perception of duration of improvement after stimulation
 - iii. Patient’s plans to continue using device
 - c. Open-ended comments
 - i. On device
 - ii. On study

Subject Payments

Participants will be given the TENS unit to keep at the successful conclusion of the study, a value of approximately \$30, to compensate for their loss of time.

Clinical vs. research purposes

The actual treatment with MNS is for clinical purposes and will be controlled by the participant. All other procedures in this study are done for research purposes.

POTENTIAL RISKS

(The language below, in this section, is addressed to the patient, as in an informed consent document.)

You may experience one or more of the risks indicated below from being in this study. In addition to these, there may be other unknown risks, or risks that we did not anticipate, associated with being in this study. You will be told of any new information that may affect your willingness to participate in this study. [name] will answer any questions you have about these risks.

MNS

Likely:

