- Severe or unstable systemic illness
- Factors (such as exaggerated symptom report) that in the judgment of the principal investigator may make the outcome measures inaccurate
- Judged by investigator to be unlikely to complete study procedures

Additional exclusion criteria were required for participation in the RCT.

CONCOMITANT MEDICATIONS

Required: none

PROHIBITED MEDICATIONS

none

TREATMENTS AND DOSAGE

TENS stimulation

- The device (TENS-7000) was judged by the FDA to be substantially equivalent to similar approved devices in the “Transcutaneous electrical nerve stimulator for pain relief” category, 501(k) premarket notification number [K080661](#).
- 12 Hz square-wave, 200 μ s pulses will be delivered over the median nerve at the wrist at the threshold for thumb movement to surface electrodes (conductive gel, 30 mm apart center-to-center, anode distal).
- The participant will determine the current delivered, using an analog knob on the TENS unit. We instruct them that we believe the stimulation has to cause thumb movement in order to be effective (based on the Nottingham EEG results), so they will likely need to adjust the current delivered each time they turn it on, given expected fluctuations in actual current delivery with changes in electrode position or electrode-skin resistance throughout the day.
- Participant can choose right or left median nerve (we will suggest their nondominant hand to minimize interference with daily activities).
- Participant will determine duration and timing of stimulation.

ANALYSIS PLAN/APPROACH/METHODOLOGY

Outcome measures

The primary outcome measures are derived from the surveys administered online throughout the study period. Surveys completed when the stimulator is turned on will assess the tic frequency and intensity prior to stimulation. For surveys where the stimulator is currently on or was recently turned off, the tic frequency and intensity will be reported in addition to discomfort and overall symptom relief. The time of each survey will be recorded in order to determine how long the device was on and the relative timing of each survey. Analysis can begin for each participant after their final survey has been completed.

Primary Outcome Measures:

1. Time spent using the device (minutes per day and number of days per week used over four-week period)
2. Do you expect to continue to use the stimulator? (yes/no/maybe, at study conclusion)

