3. Comparison of tic frequency between “turning ON” and “turning OFF” surveys (scale of 0-5)
4. Comparison of tic intensity between “turning ON” and “turning OFF” surveys (scale of 0-5)
5. Mean discomfort while using stimulator (scale of 0-3 adapted from the CGI-I Efficacy Index)
6. Relationship to blinded study results (correlation of change in tic frequency and intensity during this study as in outcome measures 3 and 4 above with change in tic frequency and intensity respectively during active, rhythmic stimulation during the RCT).

Secondary Outcome Measures:

1. What was the overall impact of the stimulation on symptoms throughout the study period? (CGI-Efficacy index)
2. How much discomfort did the stimulation cause throughout the study period? (CGI-Efficacy index)
3. Average therapeutic effect while using stimulator
4. Comparison of tic severity prior to and at the end of the study

5. Check whether reported symptom improvement across different stimulation sessions was influenced by stimulation intensity or reported discomfort
6. Comparison of tic frequency between “more than 60 minutes after turning off stimulator” and “less than 60 minutes after turning off stimulator”
7. Comparison of tic intensity between “more than 60 minutes after turning off stimulator” and “less than 60 minutes after turning off stimulator”
8. “How long do you think the improvement in your tics lasted after you turned off the device?”
9. Compare participants’ perception of tic improvement from post-study survey to their results collected during the study
10. Compare participants’ perception of length of tic improvement after turning off the stimulator from post-study survey to their results collected during the study
11. Do certain participant characteristics predict who will be “responders”?
12. Qualitative analysis of open-ended questions

Data analysis

Data storage, sharing and management. Survey data, which **will not contain PHI**, will be collected and stored on Google Forms. This data will be shared on the [Open Science Framework](#).

Overall statistical approach. To prevent “HARKing” (hypothesizing after results are known) [20], we have **registered our hypotheses** and analysis strategy on [OSF.io](#) prior to initiating enrollment. For this pilot study, all statistical tests will be reported independently, with a warning about multiplicity of tests. However, we limit the number of primary outcome measures.

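### Secondary outcome 5 asks whether stimulation intensity influenced improvement across sessions, but the protocol describes no record of the stimulation level used in any session

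*Combined protocol and SAP*

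**What the plan says.** The list of Secondary Outcome Measures (item 5) sets the task: "Check whether reported symptom improvement across different stimulation sessions was influenced by stimulation intensity or reported discomfort". It names two possible influences on improvement, stimulation intensity and discomfort, and places the question at the level of the session.

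The section on online measures during the study period lists what participants report on four occasions: turning the stimulator on (survey a), turning it off (b), answering a text with it on (c), and answering a text with it off (d). All four ask for tic intensity and tic frequency. Surveys b and c add "Discomfort from stimulation" and "Overall symptom improvement".

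The Outcome measures section describes the same surveys in prose. It says that, with the stimulator on or recently turned off, "the tic frequency and intensity will be reported in addition to discomfort and overall symptom relief". It adds one further variable: "The time of each survey will be recorded in order to determine how long the device was on".

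Under Treatments and Dosage, the participant sets the current with an analog knob. Participants are told that thumb movement is believed necessary for effect, "so they will likely need to adjust the current delivered each time they turn it on".

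**The concern.** A listed outcome should have a stated data source. For the discomfort component there is one. For stimulation intensity there appears to be none: no survey item, no end-of-study item and no described device record.

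A knob setting that is not noted at the time cannot be reliably recovered afterwards. The study is meant to inform a later controlled trial of chronic stimulation, and participants control the current themselves, so whether level relates to benefit is a reasonable question to ask. The protocol also says its hypotheses and analysis strategy were registered before enrollment to guard against after-the-fact hypotheses. A listed outcome component with no data would have to be left unreported or redefined later.

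**Working it through.** The plan gives no figure to reproduce. The check sets what outcome 5 needs against everything the protocol says is collected.

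**1. What outcome 5 needs, per session:** improvement, discomfort, stimulation level.

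**2. In-study surveys (Online during study period, item 1)**

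| Survey | Entries | Discomfort | Overall improvement | Stimulation level |
|---|---|---|---|---|
| a. Turning on | 2 | no | no | no |
| b. Turning off | 4 | yes | yes | no |
| c. Text, stimulator on | 4 | yes | yes | no |
| d. Text, stimulator off | 2 | no | no | no |

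Total entries: 2 + 4 + 4 + 2 = 12. They reduce to 4 distinct measures: tic intensity, tic frequency, discomfort and overall improvement. Adding survey time gives 4 + 1 = 5 in-study variables. Stimulation level is in 0 of the 12 entries and is not among the 5 variables. Tic intensity is a symptom rating and cannot stand in for stimulation intensity.

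**3. End-of-study items (Online at conclusion of study).** ATQ and PUTS (2); efficacy index, perceived duration of improvement and plans to continue (3); comments on the device and on the study (2). Total 2 + 3 + 2 = 7, of which 0 record stimulation level.

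**4. Other possible sources**

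- *First-visit threshold (First visit, item 6).* The current is raised from zero, "starting at 0 and increasing slowly until a twitch of the thumb is seen". This is done before home use, is not said to be recorded, and gives at most one value per person. Because the current is expected to be readjusted at each use, one baseline value cannot describe later sessions.
- *Imported data (First visit, item 2).* All data from the earlier RCT "study will be imported for comparison with information collected during this study". They come from the earlier study and contain no home sessions.
- *Device log.* None is described. Even the time the device was on is derived from survey times, and the only store named for survey data is Google Forms.
- *Open-ended comment on the device.* One free-text entry at study end, not one per session.
- *Analysis text for Aim 2.* It does not mention stimulation intensity, so it points to no source either.

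**5. Result.** Of the two predictors in outcome 5, discomfort has a stated per-session source and stimulation intensity does not: 1 of 2.

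**The case against.** The strongest reply is that the protocol lists what is measured and does not reproduce the form. The Google Form itself and the OSF registration are outside these documents, and either could hold a per-session setting. That stands as a limit on the conclusion: the protocol states no source, which is not proof that the data do not exist. Nothing in the text points to such an item, however.

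A second reply is that recording the knob setting might not rescue the outcome. Stimulation is meant to be given at the threshold for thumb movement, and readjustment is expected because electrode position and skin resistance vary. If participants comply, intensity relative to threshold is roughly constant, and the knob position mainly reflects those fluctuations. This also stands. It makes deleting the component a respectable alternative to adding an item, but it does not supply the missing data.

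Third, improvement is rated in both surveys b and c, and survey b also feeds primary outcomes, so lengthening it carries some risk of non-response. An item in b gives one setting per session, which is enough for a session-level question. It would not cover mid-session ratings from c or a knob changed partway through a session. The burden is real but small.

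Finally, the study is exploratory, and this is half of one item in a list of 12. That bears on weight only.

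**Conclusion.** The concern holds. Followed as written, the protocol collects nothing from which the intensity component of secondary outcome 5 could be analysed. The scope is one component of 1 of 12 secondary outcomes, and 0 of the 6 primary outcomes use stimulation level. The discomfort component can be computed from the surveys, although the analysis text gives no method for outcome 5 with either predictor, and without a level record an association with discomfort could not be separated from one with intensity.

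The conclusion assumes that the itemised survey and end-of-study lists are complete, as the protocol presents them. It is limited to what the protocol states. Severity is minor.

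**What to change.** Any one of three changes would close the gap:

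1. **Name the source.** If the online form or the OSF registration already includes a per-session setting, say so in the protocol. This costs one sentence.
2. **Collect it.** Add two items to the turning-off survey: the knob setting used, and whether the thumb moved (yes/no). Survey b goes from 4 to 4 + 2 = 6 items, and the listed entries from 12 to 12 + 2 = 14. If ratings from survey c are also to be used, the items belong there too. The analysis should account for repeated sessions within a participant; a participant random effect with within-person-centred predictors is one option.
3. **Remove it.** Delete the three words that bring stimulation intensity into outcome 5 and keep the discomfort component.

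The second option needs a protocol amendment and slightly lengthens a survey that also supplies primary data. Its yield may be modest: the knob setting is only a proxy for delivered current, and the thumb-movement answer may nearly always be yes if participants act on what they are told. Any result would be exploratory. If data collection is already over and no setting was recorded, the intensity component should be reported as not assessable.

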Aim 1 (determining real-world utility of stimulation). Descriptive data regarding the duration of use of the device will be reported as the mean and standard deviation of minutes per day, as well as the mean number of days used per participant. Answers to the question, “if you had a free stimulator, would you continue to use it after the study finishes?” will be reported as percentages answering “yes,” “no,” and “maybe.” Additionally, a summary of common themes to the open-ended questions about the device will be reported.

Aim 2 (determining momentary self-rated efficacy and side effects of stimulation). Comparisons of tic frequency and intensity ratings immediately prior to and following use of the simulator will be reported as paired t-tests. A similar analysis will be completed for ratings of frequency and intensity made less than 60 minutes after turning off the stimulator vs. more than 60 minutes after turning off the stimulator (unpaired t tests). Average discomfort and average therapeutic effect while using the stimulator will be reported descriptively as percentage of participants choosing each rating. A similar analysis will be conducted on average discomfort and average therapeutic effect over the entire study period as reported in the final survey. Additionally, the discomfort and therapeutic ratings collected throughout the study will be compared with those taken at the end of the study. Participants’ scores on the ATQ (adult tic questionnaire) and PUTS scale (premonitory urge for tic scale) before and after the study will be compared using the paired t-test. Participants’ responses to the question “How long do you think the improvement in your tics lasted after you turned off the device?” will be reported as percent of participants choosing each option, and these perceptions will be compared with their numerical ratings throughout the study. Finally, we will determine if certain factors have a significant impact on who is a “responder” to the device, as measured by those participants with a greater than 25% reduction in tic frequency or intensity during stimulation. The factors to be examined include

age, sex, baseline YGTSS, complex tics ever, phonic tics ever, baseline ADHD severity, and baseline OCD severity.

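### As written, the under-60-minute window in secondary outcomes 6 and 7 admits every switch-off survey, so a momentary effect could be read as carry-over

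*Combined protocol and SAP*

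**What the plan says.** Secondary outcome 6 reads "Comparison of tic frequency between “more than 60 minutes after turning off stimulator” and “less than 60 minutes after turning off stimulator", and outcome 7 is the same for intensity. Under Data analysis, Aim 2 sets "ratings of frequency and intensity made less than 60 minutes after turning off the stimulator" against later ratings by unpaired t test. Neither place lists the eligible surveys or gives a lower limit on time since switch-off.

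The ratings come from four kinds of survey:

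- **Switch-on and switch-off (a and b).** The overview of participation says "they will fill out brief surveys whenever they turn the device on and off". The section on online measures during the study period puts tic intensity and frequency in both.
- **Prompted (c and d).** "Texts will be sent twice daily at predetermined times". The reply depends on the state of the device. Survey d, "Answering a text, stimulator currently off", is the only prompted survey that can fall between minute 0 and minute 60.

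The Outcome measures text has a group described as "For surveys where the stimulator is currently on or was recently turned off", which also rates discomfort and relief. In the survey schedule, the only device-off survey with those items is the switch-off survey.

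On usage, Treatments and dosage says "Participant will determine duration and timing of stimulation". Outcome 10 reads "Compare participants’ perception of length of tic improvement after turning off the stimulator from post-study survey to their results collected during the study" and names no time window.

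**The concern.** The switch-off rating describes tics at the end of stimulation. Primary outcomes 3 and 4 use it for exactly that, as the post-use half of the before-and-after comparison. If it also enters the early window of outcomes 6 and 7, the same rating is counted once as momentary benefit and again as benefit that lasts. Most switch-on ratings, meanwhile, would fall in the later window, so the comparison would partly repeat the primary one.

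The ratings that could separate persistence from momentary effect are those made some time after switch-off. Two fixed texts a day will seldom land in that hour. A purely momentary effect could then be reported as outlasting stimulation. The Objectives note that benefit outlasted stimulation in some participants of the earlier laboratory study, and say the results should inform a controlled trial of chronic stimulation. A mistaken answer on duration could therefore carry forward.

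**Working it through.** **The plan's own figure.** The plan gives none for this comparison. Its only design figure is 75% power for a 25% reduction with 32 participants, one-tailed, without alpha or SD. At one-sided 0.05, d = (1.645 + 0.674)/√32 = 0.41, which implies an SD of change of 25/0.41 = 61%. This can be neither confirmed nor refuted, and it does not bear on the window.

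**Step 1: who fills the early window.** Per session, let c_off and c_text be the completion rates of switch-off surveys and texts, W the waking hours over which the two texts fall, and g the completed switch-on surveys made within 60 minutes of the previous switch-off. Two texts a day comes from the plan; the other values are assumptions.

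Share of switch-off surveys = c_off / (c_off + 2·c_text/W + g)

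| Assumptions | Calculation | Share |
|---|---|---|
| Full completion, g = 0, W = 12 | 1/(1 + 0.167) | 86% |
| Full completion, g = 0, W = 16 | 1/(1 + 0.125) | 89% |
| g = 0.25, W = 14 | 1/(1 + 0.143 + 0.25) | 72% |
| g = 0.5, W = 14 | 1/(1 + 0.143 + 0.5) | 61% |
| c_off = 0.3, c_text = 1, g = 0, W = 12 | 0.3/(0.3 + 0.167) | 64% |
| c_off = 0.3, c_text = 0.8, g = 0, W = 16 | 0.3/(0.3 + 0.1) | 75% |

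The share passes half when c_off exceeds 2·c_text/W + g. Moving one factor at a time with W = 14, it drops below half only if g exceeds 1 − 0.143 = 0.86, or c_off falls below about 0.14. Moderate values of both together reach half sooner: at c_off = 0.5, the limit is g = 0.5 − 0.143 = 0.36.

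**Step 2: what that does to the comparison.** The simulation had 32 participants, 28 days, a 14-hour day, texts at fixed times, 80% completion, ratings from 0 to 5 and zero true carry-over. The drop at switch-off was 0.30 points, or 0.625 points (25% of an assumed mean of 2.5). Each setting had 40 replicates. Differences are early minus late ratings, for 30- and 60-minute sessions.

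| Sessions/day | Switch-off share | Drop 0.30 | Drop 0.625 | Fraction of drop |
|---|---|---|---|---|
| 1 | 82–83% | −0.234, −0.246 | −0.501, −0.510 | 78–82% |
| 2 | 79% | −0.236, −0.234 | −0.487, −0.484 | 77–79% |
| 4 | 73% | −0.209, −0.215 | −0.443, −0.450 | 70–72% |

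The extremes of the last column are 0.209/0.30 = 70% and 0.246/0.30 = 82%. With 30% switch-off completion (two 30-minute sessions a day, drop 0.625), the share was 59% and the difference −0.352, or 56% of the drop.

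The plan does not say whether the test is on ratings or on participants. With ratings pooled, every replicate with a drop was significant. On participant means, two groups of 32 with an assumed SD of 0.65, two-sided power for spurious differences of 0.235 and 0.49 is about 30% and 85%.

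**Step 3: when no artefact arises.** With no drop at switch-off and no other reporting difference, the simulated difference was −0.012 to +0.008. A raised rating at switch-on can act alone: a 0.5-point elevation with no drop at switch-off gave −0.210.

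**Step 4: removing the switch-off survey.** The difference became −0.016 to +0.008 across the 18 main settings, with rejection rates of 0 to 12.5%. With the 0.5-point switch-on elevation it was −0.028.

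**The case against.** **The plan may mean text replies only.** Aim 2 moves from a paired test for ratings around use to an unpaired test here, which fits a different, unmatched set of ratings, and survey d has no other clearly named comparison. The plan also says its analysis strategy is registered elsewhere, and that record is not available here. This stands as a possible intention. But the text does not say it, and the Outcome measures wording groups the recently-off survey with the stimulator-on surveys, which points the other way.

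**Stronger readings a reader might infer.** One is that outcomes 6 and 7 would show carry-over whatever the truth. The documents do not support that: Step 3 shows that a difference in ratings at switch-off or switch-on is needed. Another is that outcome 10 would validate participants' impressions against the same artefact. Neither the outcome list nor Aim 2 ties outcome 10 to the 60-minute split. A third is that nearly nine in ten early ratings must be switch-off surveys. That assumes full completion and no quick restarts, neither of which the documents state.

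**Importance.** These are secondary outcomes in an exploratory convenience sample, reported with a multiplicity warning. Duration of benefit is not named in the three aims. Survey times are recorded and the data are to be shared, so the split can be redone. This limits the harm, but leaves the stated comparison biased whenever ratings drop at switch-off.

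**Conclusion.** The point holds for secondary outcomes 6 and 7. Followed as written, the rule puts the minute-0 rating into the early window, where it is usually the majority: roughly 60 to 89% over the plausible range. It falls below half only with very frequent restarts within the hour, very low switch-off completion, or a moderate combination of the two. If ratings are lower at switch-off and true persistence is zero, most of that drop is transferred to the persistence comparison: about 70 to 82% at 80% completion, and 56% in the low-completion case. These sizes rest on assumed usage, completion and rating distributions. Whether the artefact reaches significance depends on the unstated unit of analysis. Outcome 10 is underspecified and shares the problem only if it adopts the same split.

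**What to change.** State in Aim 2 that the switch-off survey does not enter the early window for outcomes 6 and 7, nor for outcome 10 if that uses the 60-minute split. Keep it in primary outcomes 3 and 4. Switch-on surveys may remain in the main analysis, since excluding the switch-off survey alone removed nearly all the simulated bias. Report an analysis restricted to survey d as a sensitivity analysis for their handling.

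The cost is a sentence or two and no new data. The downside is precision: in the simulated settings the early window shrinks from about 800–3,420 ratings study-wide to about 140–920, of which about 100–320 are text replies. The sensitivity analysis would rest on those replies alone.

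### Ratings under and over 60 minutes after switch-off come from the same participants but are compared with unpaired t-tests, so the p-values do not hold their nominal level

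*Combined protocol and SAP*

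**What the plan says.** In Data analysis, Aim 2, tic frequency and intensity are compared for ratings "less than 60 minutes after turning off the stimulator vs. more than 60 minutes after turning off the stimulator (unpaired t tests"). These are secondary outcomes 6 and 7, where one of the two windows is "less than 60 minutes after turning off stimulator".

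The ratings come from one open-label group. Participants "fill out brief surveys whenever they turn the device on and off, as well as at two other points throughout the day" (Study Design, overview of participation). The amount of use is self-chosen: "Participant will determine duration and timing of stimulation" (Treatments and Dosage).

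The neighbouring comparisons in the same people are paired. For the ON/OFF ratings, those "immediately prior to and following use of the simulator will be reported as paired t-tests". The ATQ and PUTS scores "before and after the study will be compared using the paired t-test". The post-switch-off comparison is introduced as similar to the ON/OFF one, and is then made unpaired.

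**The concern.** The two windows are two conditions within each person, not two groups of people. An unpaired t-test treats every observation as independent. That fails if the unit is the single rating, because one person gives many correlated ratings. It also fails if the unit is the participant mean, because each person contributes a mean to both windows.

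Outcomes 6 and 7 are the rating-based tests of whether tics differ by time since switch-off. Outcomes 8 and 10 approach duration through recall, and the plan sets that recall against the ratings. The Objectives section says the results are meant to inform a later controlled trial. With pooled ratings, a heavy user with severe tics weights the early window and a light user with mild tics the late one, so the test can report a difference that only reflects who uses the device more. With unpaired means, differences in severity between people can hide a real within-person difference.

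**Working it through.** **The plan's own figure.** No power or error rate is given for this comparison. The only power statement is 75% for a 25% improvement with 32 participants, one-tailed. It gives no SD or alpha, so it cannot be reproduced. At an assumed alpha of 0.05 it implies a standardised change of 0.42, that is an SD of 25/0.42 ≈ 60 percentage points. It does not bear on outcomes 6 and 7.

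**Inputs.** From the documents: 32 participants, one group, and two texts a day for 28 days (2 × 28 = 56 prompts), plus a survey at every switch-on and switch-off. Assumed, because the documents do not say: 45 off-stimulator ratings per person, 20% of them within 60 minutes on average, total rating variance 1, intraclass correlation (ICC) 0.3, 0.5 or 0.7, two-sided 5%. The early share varies between people as Beta(1,4) (wide), Beta(4,16) (moderate), Beta(10,40) (narrow), or is 20% for all.

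**Reading 1: all ratings pooled.** With m ratings per person and early share distributed as Beta(a,b), let κ = 1/(a+b+1). The true variance of the difference, divided by the variance the unpaired test assumes, is approximately

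V = 1 + ICC × κ × (m − 1), and the true type I error ≈ 2Φ(−1.96/√V).

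Example, wide mix, ICC 0.3: κ = 1/6, V = 1 + 0.3 × 44/6 = 3.20, 1.96/√3.20 = 1.10, error 27%.

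| Early share | κ | V at ICC 0.3 / 0.5 / 0.7 | Error, formula | Error, simulated |
|---|---|---|---|---|
| Wide | 1/6 | 3.20 / 4.67 / 6.13 | 27 / 36 / 43% | 29 / 37 / 43% |
| Moderate | 1/21 | 1.63 / 2.05 / 2.47 | 12 / 17 / 21% | 12 / 18 / 22% |
| Narrow | 1/51 | 1.26 / 1.43 / 1.60 | 8 / 10 / 12% | 8 / 9 / 12% |
| Same for all | 0 | 1 | 5% | about 5% |

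The simulations used 2000 to 3000 replicates per cell. Over the three varying mixes, 20 ratings per person give 6% to 26% and 90 ratings give 12% to 56%. Rounding to the 0–5 scale changes little (7% to 40%). A separate simulation with other inputs (30% early, 20 or 40 ratings on average) gave 11% to 31% with moderate variation and 25% to 54% with wide variation. At ICC 0 the error was nominal.

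**Reading 2: one mean per participant per window, unpaired.** With correlation ρ between a person's two means, and equal variances, the true variance of the difference is (1 − ρ) times the assumed one. Averaging makes ρ large. With 45 × 0.20 = 9 early and 36 late ratings at ICC 0.3, the two means have variances 0.3 + 0.7/9 = 0.378 and 0.3 + 0.7/36 = 0.319, so ρ = 0.3/√(0.378 × 0.319) = 0.86. The test uses a standard error of √((0.378 + 0.319)/32) = 0.148, while the true one is √((0.7/9 + 0.7/36)/32) = 0.055. The type I error is about 0%. A difference must exceed about 2.00 × 0.148 = 0.30 to be declared, so a true 0.3 SD effect is found only about half the time.

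Simulated power for a 0.3 SD effect, over the three varying mixes:

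| | ICC 0.3 | ICC 0.5 | ICC 0.7 |
|---|---|---|---|
| Participant means, unpaired | 41–52% | 16–17% | 3–5% |

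The paired test on the same means has type I error of 4% to 6% and power of 94% to 100% over all these ICCs, or 84% to 99% if the effect varies between people with SD 0.3.

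**Does anything else in the plan repair this?** No. The Outcome measures and Data analysis sections specify no mixed model, GEE, clustered standard error or participant-level averaging for this comparison. The warning about multiplicity does not concern dependence. The nonparametric fallback is triggered by non-normality due to outlying values.

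**The case against.** - **A third reading exists.** The test could be run separately within each participant, where early and late ratings have no natural partner and an unpaired test is the ordinary choice. The plan does say that analysis may start person by person. But the comparison is presented as similar to a group-level paired test and no per-person result is described, so this reading is unlikely. It does show that the unit of analysis should be stated.
- **Ratings do not match one to one.** That rules out pairing rating by rating. It does not make the ratings independent, and participant means or a mixed model cope with unequal counts.
- **The size rests on assumptions.** This stands. Pooled error is about 5% if everyone has the same early share, and unpaired means err on the safe side for false positives. The power loss is about half at ICC 0.3 and most of the power only at 0.5 to 0.7. At ICC 0.1 it is small (78–94% against 89–99%), with pooled error of 6–14%. The plan also does not say whether the survey made at switch-off counts as early, which would change the early share.
- **These are two of twelve secondary outcomes in an exploratory open-label study.** True, and no primary outcome depends on them. An exploratory label excuses low power or uncorrected multiplicity, but not a p-value from a test whose main assumption the design breaks.

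**Conclusion.** The concern holds. The plan names a test that does not fit its own design, and it pairs the adjacent comparisons in the same people. The p-values for outcomes 6 and 7 will generally not hold their nominal level, and the documents do not fix the direction. If ratings are pooled, the test is anti-conservative whenever ratings are correlated within people and early shares differ between them. Self-chosen use makes such differences likely. The error is then 8% to 43% under the main assumptions and 6% to 56% over 20 to 90 ratings per person. If participant means are compared unpaired, false positives almost vanish and power for a 0.3 SD effect falls to 3% to 52%. The ICC, rating counts, early shares and alpha are all assumed. The consequence is confined to the question of how long benefit lasts, so this should be fixed but does not threaten the primary outcomes.

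**What to change.** In Data analysis, Aim 2, replace the unpaired t-tests for outcomes 6 and 7 with a within-participant analysis, and state the unit of analysis. Either of these will do:

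1. a paired t-test on each participant's mean rating in each window; or
2. a linear mixed model on the ratings with a random participant intercept and a random window effect, which keeps people with ratings in only one window.

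The random window effect matters if the effect differs between people. At an assumed between-person SD of 0.3, a random intercept alone has type I error of 16% to 29%. Fitted models gave 18% without the random window effect and 4.8% with it (397 replicates). At SD 0.10 to 0.15 the intercept-only error is about 6% to 13%.

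Say whether the switch-off survey belongs to the early window, and report how many participants have ratings in only one window. If the nonparametric fallback is used, make it the Wilcoxon signed-rank test.

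The cost is a wording change and slightly more programming, with no new data. The paired version loses participants with ratings in only one window: about 0 to 3 of 32 at 45 ratings per person and 1 to 5 of 32 at 20, under the same assumptions.
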